5.7 Study Drug Dose and Administration

Complete instructions for dispensing and administering study drug are presented in the study-specific Pharmacy Manual.

Following randomization on Day 1, subjects will receive the first dose of EDP-938 or placebo orally while at the study site. After the first dose, subjects will be instructed to take the study drug orally QD on each of the 20 subsequent days. Subjects will be instructed to take the study drug at approximately the same time every day (\pm 1 hour).

Study site visits should be scheduled close to the time that the subject normally takes the study drug so that dosing can occur at the site. If a visit occurs within 4 hours of the scheduled dosing time, the subject should take the study drug at the site during the visit. If a visit occurs more than 4 hours before or after the scheduled dosing time, the subject should take study drug at the

scheduled time at home. The time and date of doses of study drug taken at the study site should be recorded by site staff in source.

If a subject forgets to take their study drug at the scheduled time, the dose should be taken as soon as the subject remembers; however, the following rules apply:

- No more than one dose should be taken on any calendar day and
- There must be a minimum of 16 hours between doses.

Site staff will record the time and date of all study drug doses taken at the site. Subjects that took study drug at home on the day of a study visit should be asked for the time that dose was self-administered and record it in the electronic case report form (eCRF).

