8.6 Pharmacokinetic Samples

Blood (plasma) samples for PK analysis will be collected as outlined in the SoA ([Appendix 1](#)).

On Day 1, Day 7, and Day 21, two samples will be collected: one predose, collected within 1 hour before dosing (preferably within 30 minutes of dosing if possible) and at the same approximate time as that of the nasopharyngeal swab collection; and one postdose sample collected 1 to 3 hour post dose.

At all other visits, one predose plasma PK sample will be collected at the same approximate time as that of the nasopharyngeal swab collection. Subjects who discontinue treatment before completing 21 days of dosing should return to the study site within 24 hours from the last dose of study treatment to complete an EOT visit. One plasma PK sample will be collected at the same approximate time as that of the nasopharyngeal swab collection.

The time and date of PK sample collection should be recorded in source and in the eCRF. Study drug (EDP-938 or placebo) should be administered during the study visit on days when clinic visits occur. Study visits should be scheduled close to the time that the subject normally takes the study drug so that dosing expected on the day of the visit can occur during the visit. In addition, the site should record the date and time of last dose taken before the PK sample collection. See Section [5.7](#) for additional dosing details.

Blood samples will be collected and processed to measure plasma concentrations of EDP-938 [REDACTED] according to the procedures provided and/or approved by Enanta Pharmaceuticals, Inc. Additional details will be provided in the Laboratory Manual.

EDP-938 [REDACTED] in human plasma will be quantified by high-performance liquid chromatography with tandem mass spectrometric detection. The method will be fully validated by assessment of precision, accuracy, sensitivity, and specificity of EDP-938 [REDACTED] by the laboratory selected by Enanta Pharmaceuticals, Inc.

Pharmacokinetic samples may be stored and used for [REDACTED] and/or further evaluation of the bioanalytical method. These data will be used for internal exploratory purposes and will not be included in the clinical study report (CSR).

8.7 [REDACTED]

[REDACTED]

[REDACTED]

[REDACTED]

[REDACTED]

[REDACTED]

[REDACTED]

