4.4 Data Handling Strategy

4.4.1 Study Days and Visit Windows

Study day is defined as the number of days from the date of first dose. Day 1 is the date of the first dose. For assessments or events that occur after the first dose date, study day is calculated as the date of interest minus first dose date plus 1 day. For assessments or events that occur before the first dose date, study day is calculated as the date of interest minus the first dose date.

Analysis visit windows are described in the tables below. Analysis visits are based on nominal scheduled visits and will be used for by-visit analyses or summaries unless otherwise specified in the respective analysis sections. Unscheduled visits and visits performed for early discontinuation will not be included in the by-visit summary or analyses.

- Unscheduled visits including repeat central laboratory assessments for the EOS visit to follow an AE for resolution will not be included in the by-visit analyses/ summaries, but will be included in the listings and other types of analyses/summaries as applicable (e.g. AUC, time to event and treatment emergent safety abnormalities any time post-baseline). For subjects who discontinues study treatment, they should complete a EOT visit and this visit will be labeled as “Early Disc/EOT”. For these subjects, they should also complete FU1 visit and FU2 visit, and these visits will be labeled as “Early Disc/FU1” and “Early Disc/FU2”.
- For subjects who completes study treatment and discontinues study before Day 28, they should complete FU1 visit and this visit will be labeled as “Early Disc/FU1”. For subjects who discontinues study between Day 28 and Day 49, they should complete FU2 visit and this visit will be labeled as “Early Disc/FU2”.

[figure not shown]
Vital signs and safety laboratory tests:

[figure not shown]
Analysis Visit #	Analysis Visit Label	Target Day	Derivation
1	Day 1	1	Based on nominal visit of V1
4	Day 4	4	Based on nominal visit of V2
7	Day 7	7	Based on nominal visit of V3
11	Day 11	11	Based on nominal visit of V4
16	Day 16	16	Based on nominal visit of V5
21	Day 21	21	Based on nominal visit of V6 if subject completes treatment

28	Day 28	28	Based on nominal visit of FU V1 if subject completes treatment and last visit is FU V2.
97	Early Disc/EOT	NA	Based on nominal visit of V6 if subject discontinues treatment
98	Early Disc/FU1	NA	Based on nominal visit of FU V1 if subject discontinues treatment or last visit is FU V1.

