RSV viral load by both RT-qPCR and CRIA:

Analysis Visit #	Analysis Visit Label	Target Day	Derivation
1	Day 1	1	Based on nominal visit of V1
4	Day 4	4	Based on nominal visit of V2
7	Day 7	7	Based on nominal visit of V3
11	Day 11	11	Based on nominal visit of V4
16	Day 16	16	Based on nominal visit of V5
21	Day 21	21	Based on nominal visit of V6 if subject completes treatment
28	Day 28	28	Based on nominal visit of FU V1 if subject completes treatment and last visit is FU V2.
49	Day 49	49	Based on nominal visit of FU V2 if subject completes treatment and study
97	Early Disc/EOT	NA	Based on nominal visit of V6 if subject discontinues treatment
98	Early Disc/FU1	NA	Based on nominal visit of FU V1 if subject discontinues treatment or last visit is FU V1.
99	Early Disc/FU2	NA	Based on nominal visit of FU V2 if subject discontinues treatment or study.

ECG:

Analysis Visit #	Analysis Visit Label	Target Day	Derivation
-1	Screening	-1	Based on nominal visit of Screening
4	Day 4	4	Based on nominal visit of V2
11	Day 11	11	Based on nominal visit of V4
21	Day 21	21	Based on nominal visit of V6 if subject completes treatment.
28	Day 28	28	Based on nominal visit of FU V1 if subject completes treatment and last visit is FU V2.
97	Early Disc/EOT	NA	Based on nominal visit of V6 if subject discontinues treatment
98	Early Disc/FU1	NA	Based on nominal visit of FU V1 if subject discontinues treatment or last visit is FU V1.

PK:

Analysis Visit #	Analysis Visit Label	Target Day	Timepoint* Assessment	Derivation
1	Day 1	1	1	Based on nominal visit of V1
1	Day 1	1	2	Same as above
4	Day 4	4	1	Based on nominal visit of V2
7	Day 7	7	1	Based on nominal visit of V3
7	Day 7	7	2	Same as above
11	Day 11	11	1	Based on nominal visit of V4
16	Day 16	16	1	Based on nominal visit of V5

21	Day 21	21	1	Based on nominal visit of V6 if subject completes treatment
21	Day 21	21	2	Same as above
97	Early Disc/EOT	NA		Based on nominal visit of V6 if subject discontinues treatment

* On Day 1, Day 7, and Day 21, two plasma PK samples will be collected (one predose and one postdose) and thus are assigned as Timepoint 1 and 2. At all other visits, only predose samples will be collected.

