8.4 PK Endpoints

8.4.1 Plasma PK concentrations of EDP-938 [REDACTED]

On Day 1, Day 7, and Day 21, two samples will be collected: one predose, collected within 1 hour before dosing (preferably within 30 minutes of dosing if possible); and at the same approximate time as that of the nasopharyngeal swab collection and one postdose, collected 1 to 3 hours postdose. At all other visits (Days 4, 11, and 16), one predose plasma PK sample will be collected at the same approximate time as that of the nasopharyngeal swab collection. Time and date of collection will be recorded on the Plasma PK Sample Collection eCRF.

For subjects in the PK analysis set, the concentration data for EDP-938 and each [REDACTED] will be summarized by visit (Days 1, 4, 7, 11, 16, and 21) and timepoint (predose or postdose). Concentrations that are below the limit of quantitation (BLQ) will be treated as zero for the computation of descriptive statistics. If more than 50% of subjects have concentration values below BLQ, descriptive statistics will not be presented except for maximum and BLQ will be displayed for mean and minimum. The number of observations, arithmetic mean, SD, % coefficient of variation (%CV), median, minimum, maximum, geometric mean, and %CV of the geometric mean (%GCV) will be displayed.

Individual data will be presented in a listing.

9 Safety Analysis

All safety analyses will be conducted using the Safety (SAF) population, where subjects will be analyzed according to the treatment actually received.

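### PK samples are labelled predose or postdose by scheduled visit, so a sample drawn after a home dose can enter the predose summary

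*SAP*

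**What the plan says.** **SAP.** Section 4.4.1 sets the general rule: "Analysis visits are based on nominal scheduled visits and will be used for by-visit analyses or summaries". The PK table in that section derives each visit from its nominal counterpart. Its footnote says that on Days 1, 7 and 21 "two plasma PK samples will be collected (one predose and one postdose) and thus are assigned as Timepoint 1 and 2", and then "At all other visits, only predose samples will be collected". Under section 8.4.1 the concentrations "will be summarized by visit (Days 1, 4, 7, 11, 16, and 21) and timepoint (predose or postdose").

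**Protocol.** Section 5.7 has two branches. In the first, "If a visit occurs within 4 hours of the scheduled dosing time, the subject should take the study drug at the site". In the second, "If a visit occurs more than 4 hours before or after the scheduled dosing time, the subject should take study drug at the" scheduled hour at home. Section 5.7 also provides for the result: "Subjects that took study drug at home on the day of a study visit should be asked for the time that dose was self-administered", and that time goes into the eCRF. Section 8.6 states the usual expectation: "Study drug (EDP-938 or placebo) should be administered during the study visit on days when clinic visits occur". It asks for visits to be booked near the subject's normal dosing time and refers to section 5.7 for further detail.

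**The concern.** A nominal label is safe only if the event it refers to always falls in the planned order. Here it need not. A subject who doses at 07:00 and is seen at 13:00 has followed section 5.7 correctly and arrives about 6 hours after the dose. No sample at that visit can be predose, but the SAP's labels make the only sample (Days 4, 11, 16) or the first sample (Days 7, 21) predose.

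Plasma concentration is a listed secondary endpoint (SAP 3.2.2), and Protocol 1.5 says this is the first study of the drug in HCT recipients. A mislabelled sample would raise the reported predose level and widen its spread, and the summary table would not show why.

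**Working it through.** The plan states no figure on this point, so there is nothing to reproduce. The check is mainly a comparison of texts.

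**Step 1. Which visits and which branch.** Day 1 is unaffected, because Protocol 5.7 has the first dose taken at the site. For Days 4, 7, 11, 16 and 21:

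| Visit relative to scheduled dose | Dose taken (Protocol 5.7) | First or only sample | Second sample (Days 7, 21) |
|---|---|---|---|
| Within 4 h | At the site | Before the dose; label right | 1–3 h sample possible |
| More than 4 h before | At home, later | Before the dose; label right, though well over an hour ahead of it | 1–3 h sample cannot be taken at the visit |
| More than 4 h after | At home, already taken | After the dose; **label wrong** | Normally past the 1–3 h window |

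In the last row the sample is more than 4 h after a dose taken on time. With the permitted ±1 h, a dose taken 1 h late gives more than 4 − 1 = 3 h.

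**Step 2. Does the SAP catch the last row?** Section 8.4.1 repeats the planned collection times for Days 1, 7 and 21 but does not make them a condition for entering the summary. No rule relabels or excludes a sample by its time since dosing. By contrast, SAP 8.2.1 uses the actual date and time of each swab for the viral load AUC.

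**Step 3. Weight of one sample.** SAP 4.1 gives 9 randomized and SAP 4.2 gives 2:1 allocation. Expected on active drug: 9 × 2/3 = 6. The actual split is not given. One sample is 1/6 = 17% of a visit's predose data; for 7 to 5 active subjects the share is 1/7 = 14% to 1/5 = 20%.

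**Step 4. Illustration only.** Let one of n = 6 samples be mislabelled, let its level be r times a true predose level, and let the others be equal. The arithmetic mean is multiplied by 1 + (r − 1)/6 and the geometric mean by r^(1/6):

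| r (assumed) | Arithmetic mean | Geometric mean |
|---|---|---|
| 1.5 | × 1.08 | × 1.07 |
| 2 | × 1.17 | × 1.12 |
| 3 | × 1.33 | × 1.20 |
| 5 | × 1.67 | × 1.31 |

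The available text gives neither r nor the half-life. If decline were mono-exponential at steady state with half-life h, then r = 2^((24 − t)/h) at t hours after the dose:

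- h = 12 h: r = 3.17 at t = 4 and 2.24 at t = 10.
- h = 24 h: r = 1.78 at t = 4 and 1.50 at t = 10.
- h = 48 h: r = about 1.33 at t = 4, which raises the arithmetic mean by 0.33/6, or about 6%.

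The answer therefore depends on the assumption chosen.

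**The case against.** The strongest reply is that home dosing before a visit is a fallback. Protocol 5.7, section 8.6 and the schedule footnotes all ask for visits near the dosing time so that dosing happens at the visit. The SAP's description of the Day 7 and Day 21 predose sample would not fit one drawn hours after a home dose, so a programmer might not label it predose. The PK summary is descriptive, and both individual concentrations (SAP 8.4.1) and dosing records (SAP 7.3) are listed, so a careful reader could find the discrepancy.

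Much of this stands, and it limits the impact. It does not supply the missing rule. The fallback is one the protocol itself provides for, and on Days 4, 11 and 16 the SAP says outright that only predose samples exist.

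Several stronger readings are tempting but unsupported:

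- *That postdose levels were in fact reported as troughs.* No document shows that any of the 9 subjects dosed at home before a visit, and the SAP says predose, not trough.
- *That both home-dosing branches mislabel.* An early visit gives a truly predose sample; the absent 1–3 h sample is missing data.
- *That exposure in azole users would look too high.* Nothing suggests late visits are commoner in them, and the readable PK text has no split by azole use.
- *That section 8.6 flatly contradicts section 5.7.* It states an expectation and refers to 5.7 for detail. The two still read differently on visit-day dosing.

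**Conclusion.** The gap is real but limited. As written, the SAP can place a sample drawn after the dose in the predose summary on Days 4, 7, 11, 16 or 21 whenever a visit falls more than 4 hours after the scheduled dosing time. One such sample would be about 17% of that visit's predose data, assuming 6 active subjects. The bias is upward, provided that levels after a dose exceed those just before it. A reader might take a particular percentage from the illustration as the effect of this plan; the documents do not support one, because the postdose-to-predose ratio, the actual treatment split and the number of affected samples are all unknown. No efficacy conclusion depends on the predose summary.

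**What to change.** In SAP 4.4.1 and 8.4.1, classify each PK sample from its recorded time and the recorded time of that day's dose:

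- *Predose*: only if drawn before that day's dose.
- *Postdose*: only if drawn in the protocol's 1–3 h window after it.
- *Neither*: list with actual time since last dose and leave out of both summaries.

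I would not add a minimum interval since the previous dose. With about 6 active subjects, it would discard samples that are truly predose.

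The cost is one rule and a little programming, and a few samples would leave small summary cells. Sample times and same-day home-dose times are in the eCRF. Protocol 5.7 puts the time of doses given at the site in source, and section 8.6 does not say where the last-dose time is stored, so confirm that both are in the database. Protocol 11.1 bars SAP changes after unblinding; if that has passed, give the reclassified summary in the study report, identified as an addition.

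Protocol 5.7 and 8.6 on visit-day dosing should also be reconciled. With the trial terminated, this cannot change its conduct, but it matters wherever the same text is reused.

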4.4.2 Missing Date Imputation

Imputation rules for missing or partial AE start/end dates are defined as:

- Only Day of AE start date is missing:
 - If the AE start year and month are the same as that for the first dose date, then:
 - If the full (or partial) AE end date is NOT before the first dose date or AE end date is missing, then impute the AE start day as the day of first dose date.
 - Otherwise, impute the AE start day as 1.
- If Day and Month of AE start date are missing:
 - If AE start year = first dose year, then:
 - If the full (or partial) AE end date is NOT before the first dose date or AE end date is missing, then impute the AE start Month and Day as the Month and Day of first dose date.
 - Otherwise, impute the AE start MONTH as January and the DAY as 1.
- If Year of AE start date is missing:
 - If the year of AE start is missing or AE start date is completely missing, then query site and leave as missing.
- For missing and partial adverse event end dates, imputation will be performed as follows:
 - If only the day of the month is missing, the last day of the month will be used to replace the missing day.
 - If the day and month are missing or a date is completely missing, it will be considered as missing.

Imputation rules for missing or partial medication/therapy start/stop dates are defined below:

- If only Day of CM start date is missing:
 - If the CM start year and month are the same as that for the first dose date, then:
 - If the full (or partial) CM end date is NOT before the first dose date or CM end date is missing, then impute the CM start day as the day of first dose date.

- If the full (or partial) CM end date is NOT before the first dose date or CM end date is missing, then impute the CM start day as the day of first dose date.
 - Otherwise, impute the CM start day as 1.
- If Day and Month of CM start date are missing:
 - If CM start year = first dose year, then:
 - If the full (or partial) CM end date is NOT before the first dose date or CM end date is missing, then impute the CM start Month and Day as the Month and Day of first dose date.
 - Otherwise, impute the CM start MONTH as January and the DAY as 1.
- If Year of CM start date is missing:
 - If the year of CM start is missing or CM start date is completely missing, then query site and leave as missing.
- For missing and partial CM end dates, imputation will be performed as follows:
 - If only the day of the month is missing, the last day of the month will be used to replace the missing day.
 - If the day and month are missing or a date is completely missing, it will be considered as missing.

5 Subject Disposition

5.1 Disposition

A summary of the analysis populations includes the number and percentage of subjects in each analysis population (ITT, mITT by RT-qPCR, mITT by CBIA, SAF, and PK) by treatment group and overall. The number and percentage of subjects excluded from each analysis population and the reasons for exclusion will also be presented. All percentages will be based on the number of subjects randomized.

Subject disposition will be summarized by treatment group and overall for all subjects who provided informed consent. A disposition of subjects includes the number and percentage of subjects for the following categories: subjects who were randomized, subjects who completed study treatment, subjects who discontinued study treatment, subjects who completed the study, subjects who discontinued from the study. All percentages will be based on the number of subjects randomized. The reasons for discontinuation of study treatment and study participation will also be summarized in this table.

The reason for discontinuation of study treatment or study participation may include any of the following: adverse event, lack of efficacy, lost to follow-up, pregnancy, protocol deviation, study terminated by sponsor, withdrawal by subject, physician decision, COVID-19, or other reason.

Subject disposition data and exclusions from analysis populations will also be presented in a listing.

5.2 Protocol Deviations

All protocol deviations (both significant and non-significant) were entered and tracked in [REDACTED] Clinical Trial Management System (CTMS) by the study team throughout the conduct of the study in accordance with [REDACTED] Study Deviation Rules Document. A significant deviation is any deviation that may affect primary efficacy and safety assessments (as applicable), the safety or mental integrity of a subject, or the scientific value of the trial.

Data will be reviewed by the study team prior to unblinding and closure of the database to ensure all significant deviations are captured and properly categorized.

Significant protocol deviations will be summarized by treatment group and overall based on randomized subjects. A separate listing will be provided for significant protocol deviations and non-significant protocol deviations.

6 Demographics and Baseline Characteristics

6.1 Demographics

A summary of demographics and baseline information will be presented by treatment group and overall for all subjects in the safety population.

The demographic characteristics consist of age, sex, race, and ethnicity.

The baseline characteristics consist of baseline height, baseline weight, baseline body mass index, smoking history, ribavirin treatment at screening (stratification factor), absolute lymphocyte count (ALC) at screening (stratification factor), absolute neutrophil count (ANC) on Day 1, RSV subgroup, [REDACTED] RSV viral load by RT-qPCR and CBIA, co-pathogens detected on Day 1, hospitalization status on Day 1 [REDACTED] [REDACTED]. Body mass index is calculated as (body weight in kilograms) / (height in centimeters / 100)². RSV subgroup is determined by an RSV A/B RT-qPCR assay and co-pathogens are determined by a respiratory pathogen panel at the central laboratory. The baseline RSV type category is derived by algorithm described in [Section 8.2.1](#).

Age (years), baseline height (cm), baseline weight (kg), baseline BMI (kg/m²), [REDACTED] RSV viral load as measured by RT-qPCR (log₁₀ copies/mL) and CBIA (log₁₀ PFU/mL) will be summarized using descriptive statistics. The number and percentage of subjects by age group (< 65, ≥ 65 years), sex (Male, Female), race (White, African American, Asian, American Indian or Alaska Native, Native Hawaiian or Other Pacific Islander, Other), ethnicity (Hispanic or Latino, Not Hispanic or Latino), smoking history (Current, Previous, Never), ribavirin treatment at screening (Present, Absent), ALC at screening (<200, ≥200 cells/µL), ANC on Day 1 (<500, ≥500 cells/µL), RSV subgroup (RSV A, RSV B, Undetectable, Missing), co-pathogens detected on Day 1 (e.g., Adenovirus, Parainfluenza virus, SARS-CoV-2), hospitalized on Day 1 (Yes,

No), [REDACTED], and subjects with any medical conditions will also be reported. Percentages will be based on the total number of subjects in the safety population.

Subject demographic and baseline characteristics will also be presented in a listing. Additionally, the RSV test information collected at screening (i.e. RSV test date, RSV test type, manufacturer name of RSV test, RSV test result, number of days between RSV test and first dose) will be presented in a separate listing.

